11 CLINICAL MONITORING

Clinical Monitoring will be conducted to ensure that the rights and well-being of trial subjects are protected, that the reported trial data are accurate, complete, and verifiable. Clinical Monitoring also ensures conduct of the trial is in compliance with the currently approved protocol, ICH, GCP, and applicable regulatory requirements. Clinical monitoring will also verify that any critical study procedures are completed following specific instructions in the protocol-specific Manual of Procedures (MOP).

Monitoring for this study will be performed by a designated independent monitor(s). Details of clinical site monitoring are documented in a Clinical Monitoring Plan (CMP). The CMP describes in detail who will conduct the monitoring, at what frequency monitoring will be done, at what level of detail monitoring will be performed, and the distribution of monitoring reports. Monitoring visits will include, but are not limited to, review of regulatory files, source data, eCRFs, ICFs, medical and laboratory reports, study record storage, training records, and protocol and GCP compliance. Site monitors will have access to study staff and all study documentation. Study monitors will meet with the PI to discuss any problems and outstanding issues and will document site visit findings and discussions.

Quality Assurance and Quality Control

To ensure the reliability of study data, the site will develop a Clinical Quality Management Plan (CQMP). The CQMP will describe:

- Routine internal quality control (QC) and quality assurance (QA) activities
 - for the purposes of measuring, documenting and reporting study conduct, protocol adherence, human subjects' protections, and reliability of the protocol-driven data collected,
 - independent of sponsor site monitoring.
- A process for identifying data quality issues (i.e., data collection, recording, and reporting findings in a timely manner); systemic issues (i.e., protocol conduct, non-compliance, human subject protections), and implementation and evaluation of Corrective and Preventative Action Plan (CAPA) procedures.

The site principal investigator will provide direct access to all study-related sites, source data/data collection forms, and reports for the purpose of monitoring, auditing by the sponsor, and inspection by local and regulatory authorities. The site principal investigator will ensure all study personnel are appropriately trained and applicable documentation are maintained on site.

The data system will implement quality control procedures and generate data quality control checks that will be run on the database. Any missing data or data anomalies will be communicated to the site for clarification and resolution.

12 PUBLICATION POLICY

All investigators funded by the NIH must submit, or have submitted for them, an electronic version of their final, peer-reviewed manuscripts, upon acceptance for publication, to the National Library of Medicine's PubMed Central (<http://www.ncbi.nlm.nih.gov/pmc/>). The NIH Public Access Policy ensures the public has access to the published results of NIH-funded research. It requires investigators to submit final peer-reviewed journal manuscripts that arise from NIH funds to the digital archive PubMed Central

upon acceptance for publication. Further, the policy stipulates that these papers must be accessible to the public on PubMed Central no later than 12 months after the official date of publication.

Refer to:

- NIH Public Access Policy, <http://publicaccess.nih.gov/>
- NIH Office of Extramural Research (OER) Grants and Funding, <http://grants.nih.gov/grants/oer.htm>

Following completion of this clinical trial, the PI will publish the results of this research in a scientific journal. The International Committee of Medical Journal Editors (ICMJE) member journals have adopted a trials-registration policy as a condition for publication. This policy requires that all clinical trials be registered in a public trials registry, such as ClinicalTrials.gov (<http://clinicaltrials.gov/>), which is sponsored by the National Library of Medicine. Other biomedical journals are considering adopting similar policies.

14 APPENDIX A: GRADING OF SEVERITY FOR ADVERSE EVENTS

Abnormal vital signs will be recorded as adverse events according to the severity scores tabulated below. The table is not intended to be all inclusive and non-listed abnormal vital signs will require investigator judgement. In general, abnormal vital signs alone which are otherwise asymptomatic will not qualify as grade 4, potentially life-threatening events.

Vital Sign Parameter	Mild (Grade 1)	Moderate (Grade 2)	Severe (Grade 3)	Potentially Life-Threatening (Grade 4)
Oral Temperature*	38.1°C – 38.4°C 100.6°F – 101.1°F	38.5°C – 38.9°C 101.2°F – 102.0°F	>38.9°C >102.0°F	abnormal vital signs without other symptoms (e.g., asymptomatic grade 3 vital sign alone) cannot qualify as a grade 4 severity
SpO ₂ (%)	92-94	89-91	<89	
Tachycardia – beats per minute	100 – 130	131 – 155	>155	
Hypotension (systolic) mmHg	80 – 84	75 – 79	<75	
Hypotension (diastolic) mmHg	50 – 54	45 – 49	<45	
Respiratory Rate – breaths per minute	21-24	25-29	>30	

* Fever must be confirmed by a repeat oral temperature measurement at least 5 minutes later; no eating or drinking anything hot or cold within 5 minutes prior to taking oral temperature is necessary for a valid oral temperature measurement

The Division of AIDS (DAIDS) Table for Grading the Severity of Adult and Pediatric Adverse Events, Version 2.1 consists of parameters, or AEs, with severity grading guidance that are to be used in DAIDS clinical trials for safety data reporting to maintain accuracy and consistency in the evaluation of AEs. The EMIT-2 study intends to report AEs in general alignment with the DAIDS grading guidance. The following table contains the grading of some common or expected reactions and is not intended to be an exhaustive listing. In addition, all deaths related to an AE are to be classified as grade 5. The complete DAIDS Grading Table is at <https://rsc.niaid.nih.gov/clinical-research-sites/daids-adverse-event-grading-tables>.

Adverse Event Parameter	Mild (Grade 1)	Moderate (Grade 2)	Severe (Grade 3)	Potentially Life-Threatening (Grade 4)
Arrhythmia	No symptoms AND no intervention indicated	No symptoms AND non-urgent intervention indicated	Non-life-threatening symptoms AND non-urgent intervention indicated	Life-threatening arrhythmia OR Urgent intervention indicated
Hemorrhage	NA	Symptoms AND no transfusion indicated	Symptoms AND Transfusion of \leq 10 cc/kg of packed RBCs indicated	Life-threatening hypotension OR Transfusion of $>$ 10 cc/kg of packed RBCs indicated
Bruising	Localized to one area	Localized to more than one area	Generalized	NA
Rash	Localized rash	Diffuse rash OR Target lesions	Diffuse rash AND Vesicles or limited number of bullae or superficial ulcerations of mucous membrane limited to one site	Extensive or generalized bullous lesions OR Ulceration of mucous membrane involving two or more distinct mucosal sites OR Stevens-Johnson syndrome OR toxic epidermal necrolysis
Bloating or Distension (of abdomen)	Symptoms causing no or minimal interference with usual social & functional activities	Symptoms causing greater than minimal interference with usual social & functional activities	Symptoms causing inability to perform usual social & functional activities	NA
Constipation	NA	Persistent constipation requiring regular use of dietary modifications, laxatives, or enemas	Obstipation with manual evacuation indicated	Life-threatening consequences (e.g., obstruction)
Dysphagia or Odynophagia	Symptoms but able to eat usual diet	Symptoms causing altered dietary intake with no intervention indicated	Symptoms causing severely altered dietary intake with intervention indicated	Life-threatening reduction in oral intake

Diarrhea	Liquid stools (more unformed than usual) by usual number of stools	Liquid stools with increased number of stools OR mild dehydration	Liquid stools with moderate dehydration	Life-threatening consequences (e.g., liquid stools resulting in severe dehydration, hypotensive shock)
Nausea	Transient (<24 h) or intermittent AND no or minimal interference with oral intake	Persistent nausea resulting in decreased oral intake for 24-48 h	Persistent nausea resulting in minimal oral intake for >48 h OR Rehydration indicated (e.g., IV fluids)	Life-threatening consequences (e.g., hypotensive shock)
Vomiting	Transient or intermittent AND no or minimal interference with oral intake	Frequent episodes with no or mild dehydration	Persistent vomiting resulting in orthostatic hypotension OR Aggressive rehydration indicated (e.g., IV fluids)	Life-threatening consequences (e.g., hypotensive shock)
Arthralgia	Joint pain causing no or minimal interference with usual social & functional activities	Joint pain causing greater than minimal interference with usual social & functional activities	Joint pain causing inability to perform usual social & functional activities	Disabling joint pain causing inability to perform basic self-care functions
Arthritis	Stiffness or joint swelling causing no or minimal interference with usual social & functional activities	Stiffness or joint swelling causing greater than minimal interference with usual social & functional activities	Stiffness or joint swelling causing inability to perform usual social & functional activities	Disabling joint stiffness or swelling causing inability to perform basic self-care functions
Myalgia (generalized)	Muscle pain causing no or minimal interference with usual social & functional activities	Muscle pain causing greater than minimal interference with usual social & functional activities	Muscle pain causing inability to perform usual social & functional activities	Disabling muscle pain causing inability to perform basic self-care functions
Altered Mental Status	Changes causing no or minimal interference with usual social & functional activities	Mild lethargy or somnolence causing greater than minimal interference with usual social & functional activities	Confusion, memory impairment, lethargy, or somnolence causing inability to perform usual social & functional activities	Delirium OR Obtundation OR Coma

Ataxia	Symptoms causing no or minimal interference with usual social & functional activities OR No symptoms with ataxia detected on examination	Symptoms causing greater than minimal interference with usual social & functional activities	Symptoms causing inability to perform usual social & functional activities	Disabling symptoms causing inability to perform basic self-care functions
Seizures	Seizure lasting < 5minutes with < 24 hours postictal state	Seizure last 5 to < 20 minutes with < 24 hours postictal state	Seizure lasting ≥ 20 minutes OR > 24 hours postictal state	Prolonged and repetitive seizures (e.g., status epilepticus) OR Difficult to control (e.g., refractory epilepsy)
Syncope	Near syncope without loss of consciousness (e.g., pre-syncope)	Loss of consciousness with no intervention indicated	Loss of consciousness AND Hospitalization or intervention required	NA
Acute Bronchospasm	Forced expiratory volume in 1 sec or peak flow reduced to ≥70 to <80% OR Mild symptoms with intervention not indicated	Forced expiratory volume in 1 sec or peak flow 50 to <70% OR Symptoms with intervention indicated OR Symptoms causing greater than minimal interference with usual social & functional activities	Forced expiratory volume in 1 sec or peak flow 25 to <50% OR Symptoms causing inability to perform usual social & functional activities	Forced expiratory volume in 1 sec or peak flow <25% OR Life-threatening respiratory or hemodynamic compromise OR Intubation
Dyspnea or Respiratory Distress	Dyspnea on exertion with no or minimal interference with usual social & functional activities OR Wheezing OR Minimal increase in respiratory rate for age	Dyspnea on exertion causing greater than minimal interference with usual social & functional activities OR Nasal flaring OR Intercostal retractions OR Pulse oximetry 90 to <95%	Dyspnea at rest causing inability to perform usual social & functional activities OR Pulse oximetry <90%	Respiratory failure with ventilator support indicated (e.g., CPAP, BPAP, intubation)

Acute Allergic Reaction	Localized urticaria (wheals) with no medical intervention indicated	Localized urticaria with intervention indicated OR Mild angioedema with no intervention indicated	General urticaria OR Angioedema with intervention indicated OR Symptoms of mild bronchospasm	Acute anaphylaxis OR Life-threatening bronchospasm OR Laryngeal edema
Chills	Symptoms causing no or minimal interference with usual social & functional activities	Symptoms causing greater than minimal interference with usual social & functional activities	Symptoms causing inability to perform usual social & functional activities	NA
Fatigue or Malaise	Symptoms causing no or minimal interference with usual social & functional activities	Symptoms causing greater than minimal interference with usual social & functional activities	Symptoms causing inability to perform usual social & functional activities	Incapacitating symptoms of fatigue or malaise causing inability to perform basic self-care functions
Clinical adverse event NOT identified elsewhere in the complete grading table	Mild symptoms causing no or minimal interference with usual social & functional activities with intervention not indicated	Moderate symptoms causing greater than minimal interference with usual social & functional activities with intervention indicated	Severe symptoms causing inability to perform usual social & functional activities with intervention or hospitalization indicated	Potentially life-threatening symptoms causing inability to perform basic self-care functions with intervention indicated to prevent permanent impairment, persistent disability, or death

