6.6 Treatment of Influenza

For the healthy young adult, influenza infection is largely a self-limiting viral infection which only requires rest and supportive care. No later than 72 hours of a Recipient demonstrating any criteria which satisfy the primary outcome of SAR influenza infection and immediately upon onset of fever $>102^{\circ}\text{F}$, meeting other criteria for a grade 3 adverse event (see Appendix A), or as required by the clinical judgement of study physicians, therapeutic intervention with an approved influenza antiviral agent (i.e., oseltamivir or baloxavir marboxil) will commence. Meanwhile, the subject will be requested to provide exhaled breath specimens; the subject will not be required to participate in additional *exposure event* group activities.

Recipients that become secondarily influenza infected may provide voluntary consent to continue in the CHIVITT as a Donor; the Donor consent form must be reviewed and signed in order for the participant to

continue as a Donor. Under this circumstance, treatment with the influenza antiviral agent will be withheld and the subject (now considered an infectious subject) will be instructed to participate in *exposure event* group activities, as a Donor participant. The participant may choose to terminate their participation as a Donor participant at any time before the maximum 5 days, as originally intended for a Donor participant. Upon deciding to terminate in participation in the CHIVITT, the subject can be administered an influenza antiviral agent and may be discharged. Under all circumstances, symptoms of an influenza infection are intended to be followed to resolution and this may be done through phone call contacts upon discharge; the dates of resolution of influenza symptoms are intended to be documented.

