6.8 Escalation of Care

In rare instances a subject's illness may meet criteria for escalation of care, wherein more in-depth evaluation and/or treatment of illness may be necessary. Escalation of care may involve referral to the local Emergency Room or Urgent Care Center, as the investigator has deemed the severity of illness to be beyond the simple supportive care which can be provided by the EMIT-2 facility. Subjects infected with influenza will be monitored for the possible development of severe symptoms and any influenza complications (as outlined in [section 2.5.1](#)). If a subject has a severe influenza complication(s) or has shortness of breath with an $\text{SpO}_2 < 89\%$ or has any 2 severe grade vital signs (see [Appendix A](#) for severity grading for vital signs), then escalation of care is to be considered.

Therapeutic intervention with an approved influenza antiviral agent (oseltamivir or baloxavir marboxil) should commence immediately upon recognition that escalation of care for influenza is necessary and if not yet already initiated. Study physicians have the authority to exercise clinical judgement to initiate referral for pulmonary function testing, chest radiography, institution of supplemental oxygen, or the initiation of bronchodilators for management. Escalation of care may also include immediate referral to the local urgent care or emergency department for rapid diagnostic testing and/or management. The intent is that there will be no delay in providing appropriate escalation of care to study participants and that the study physicians document their decision-making process. UMB and/or its affiliated institutions or healthcare groups will not provide financial compensation or reimbursement for the cost of referred care that may be provided. The institution or group providing medical treatment will charge the participant's insurance carrier.

Meanwhile, the ill subject will not be required to participate in *exposure event* group activities and will be afforded the time to rest and recover or be referred for higher-level care. Participant preference is intended to be honored. However, when the investigator judges that escalation of care is necessary for the welfare of the participant then participation in *exposure event* activities will be prohibited.

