An adverse event or suspected adverse reaction is considered "serious" if, in the view of either the investigator or sponsor, it results in any of the following outcomes (21 CFR 312.32 (a)):

- death
- a life-threatening adverse event
- inpatient hospitalization or prolongation of existing hospitalization
- a persistent or significant incapacity or substantial disruption of the ability to conduct normal life functions, or
- a congenital anomaly/birth defect.

Important medical events that may not result in death, be life-threatening or require hospitalization may be considered serious when, based upon appropriate medical judgment, they may jeopardize the patient or subject and may require medical or surgical intervention to prevent one of the outcomes listed in this definition. Examples of such medical events include allergic bronchospasm requiring intensive treatment in an emergency room or at home, convulsions that do not result in inpatient hospitalization, etc.

SAEs will be:

- Assessed for severity and relationship to study intervention and alternate etiology (if not related to study intervention) only by the site Principal Investigator or Co-investigator with the training and authority to make a diagnosis.
- Recorded on the appropriate SAE data collection form and eCRF.
- Followed through resolution by a licensed study clinician.
- Reviewed and evaluated by the principal investigator, the DMID MO, MM, CPM, and the IRB/IEC.

Severity of Event

All AEs or SAEs will be assessed for severity according to the toxicity grading scales in [Appendix A](#).

For adverse events (AEs) not included in the protocol-defined grading system, the following guidelines will be used to describe severity.

- **Mild (Grade 1)**: Events that are usually transient and may require only minimal or no treatment or therapeutic intervention and generally do not interfere with the subject's usual activities of daily living.
- **Moderate (Grade 2)**: Events that are usually alleviated with additional specific therapeutic intervention. The event interferes with usual activities of daily living, causing discomfort but poses no significant or permanent risk of harm to the research participant.
- **Severe (Grade 3)**: Events interrupt usual activities of daily living, or significantly affect clinical status, or may require intensive therapeutic intervention. Severe events are usually incapacitating.

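### Appendix A gives a respiratory rate of exactly 30 no severity grade, on the moderate/severe line that three care rules use (minor)

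*Protocol*

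**What the plan says.** Appendix A opens its vital-sign table with the rule "Abnormal vital signs will be recorded as adverse events according to the severity scores tabulated below". The row "Respiratory Rate – breaths per minute" then gives 21–24 for grade 1, 25–29 for grade 2 and >30 for grade 3. The grade 4 column holds no number for any vital sign.

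Three sections use the boundary between moderate (grade 2) and severe (grade 3):

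- Section 6.6 starts an antiviral in an infected Recipient within 72 hours at the latest, but at once on a fever above 102°F or on "meeting other criteria for a grade 3 adverse event (see Appendix A").
- Section 6.8 lists several grounds for considering escalation. One is that the participant "has any 2 severe grade vital signs", graded by Appendix A.
- Section 6.9 permits discharge home only if influenza signs and symptoms are at most moderate by Appendix A. It also requires clinical stability and the participant's statement that they can look after themselves.

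**The concern.** A grading table that drives care should give every measurable value one grade. Here the uncovered value lies exactly where the table turns from moderate to severe, so the omission bears on treatment, escalation and discharge rather than on a descriptive label. Read literally, the gap errs in the permissive direction: a rate of 30 is not severe, so it triggers nothing and blocks nothing.

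The value is not an exotic one. If staff count breaths for half a minute and double the count, 15 breaths give 2 × 15 = 30. The protocol does not state the counting method, so that is an assumption. Participants are deliberately exposed to influenza without direct benefit to themselves, which is a reason to have the objective thresholds complete.

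**Working it through.** **Step 1. Compare the rows.** All inputs are from the Appendix A vital-sign table.

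| Vital sign | Grade 1 | Grade 2 | Grade 3 | Values between grades 2 and 3 |
|---|---|---|---|---|
| Temperature, °C | 38.1–38.4 | 38.5–38.9 | >38.9 | none |
| Temperature, °F | 100.6–101.1 | 101.2–102.0 | >102.0 | none |
| SpO₂, % | 92–94 | 89–91 | <89 | none |
| Heart rate | 100–130 | 131–155 | >155 | none |
| Systolic pressure | 80–84 | 75–79 | <75 | none |
| Diastolic pressure | 50–54 | 45–49 | <45 | none |
| Respiratory rate | 21–24 | 25–29 | >30 | 30 |

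The two temperature lines are one row of the table, so there are six rows. Each was enumerated in whole units (0.1 degree for temperature). Five rows have no ungraded and no doubly graded value. For respiratory rate, enumeration from 21 to 35 leaves exactly one ungraded value, 30, and none with two grades.

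**Step 2. Look for text that fills the gap.**

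- Appendix A says that "non-listed abnormal vital signs will require investigator judgement". Respiratory rate is listed, so this clause does not clearly apply.
- Section 7.2 has a fallback for adverse events "not included in the protocol-defined grading system, the following guidelines will be used to describe severity". Respiratory rate is in the grading system. Even if the fallback were applied, it grades by interference with daily activities and not by the rate.
- The only other wording on respiratory rate in Appendix A is "Minimal increase in respiratory rate for age", a grade 1 item in the dyspnea row. It sets no number.

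None of the three assigns a grade to a rate of 30.

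**Step 3. See when the grade changes a decision.** Let k be the number of other grade 3 findings present (for Section 6.8, other severe vital signs). Compare 30 as printed, not severe, with 30 treated as severe.

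- Sections 6.6 and 6.9 turn on at least one severe finding. As printed the count is k; with the correction it is k + 1. The answers differ only when k = 0 (0 against 1).
- Section 6.8 turns on at least two. The answers differ only when k = 1 (1 against 2).
- In all other cases the rules give the same answer either way.

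**Step 4. Apply the correction.** With grade 3 set to ≥30, every whole-number rate from 21 to 35 has exactly one grade, and 30 is grade 3.

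**The case against.** The strongest reply is that no participant has to be handled wrongly. Section 6.6 also starts treatment "or as required by the clinical judgement of study physicians". Section 6.8 only asks that escalation be considered and gives physicians authority to act. Section 6.9 adds clinical stability and self-care, and Section 6.5 provides an on-call physician at all hours. This stands, and it is why the point is minor. It does not remove the point, because discretion is a backstop to an explicit threshold and does not define it.

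A second reply is that Section 7.2 groups clearly related signs under a single diagnosis. A rate of 30 in a breathless participant could then be graded within a dyspnea event, by function and other signs. This stands in part. It narrows the gap mainly to a rate of 30 that is not part of such an event. It does not supply a grade for Section 6.8, which counts vital signs by their own grading.

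A third reply is that a ≥ sign may have been lost when the PDF was read. That cannot be excluded from the text alone. It is unlikely, since ≥ survives elsewhere in the same appendix, for example in the bronchospasm and seizure rows. A look at the source table would settle it.

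A reader might also infer a second contradiction in Appendix A: an SpO₂ of 89% is grade 2 among the vital signs but meets the grade 3 oximetry criterion (<90%) in the dyspnea row. The documents do not support making that a finding. Under the grouping rule in Section 7.2, the two scales can serve different events, an isolated reading and a respiratory diagnosis. Section 6.8 has its own SpO₂ cut-off, and no care rule clearly changes.

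**Conclusion.** The gap is real as printed: one whole-number value, in one of six rows, on the boundary between grades 2 and 3. Its possible effect is confined to a participant at exactly 30 breaths per minute who has no other grade 3 finding (Sections 6.6 and 6.9) or exactly one other severe vital sign (Section 6.8). Clinical judgement and the additional conditions limit it further. The severity is minor.

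The conclusion assumes that the table was read correctly from the PDF, that rates are recorded in whole breaths, and that the rules are applied literally.

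Two stronger conclusions might be drawn, and neither is supported. One is that the trial's safety oversight is compromised, for instance that the monthly review in Section 6.11 would miss severe events. Sections 7.1 and 7.2 leave it largely to the clinician whether influenza findings become adverse events, so no such loss can be shown. The other is that the trial's results are affected. The secondary attack rate does not use this table, and neither does the sample size in Section 9.2.

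**What to change.** In the Appendix A vital-sign table, change the grade 3 respiratory-rate cell from >30 to ≥30. This keeps the grade 2 band as printed and lets grade 3 begin immediately after it, as in the other rows. Extending grade 2 to 25–30 would also close the gap, but ≥30 is the more cautious choice and leaves the grade 2 band alone. The clinical team should confirm the value.

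The cost is one symbol in one cell. The downside is at most slightly more readings graded severe. Sections 6.6, 6.8 and 6.9 need no rewording, because they refer to Appendix A.
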